6.1. Adverse event definitions

The term “adverse event” could include any of the following events which develop or increase in severity during the course of the study, after administration of the study product:

- Any unfavourable and unintended signs, symptoms or disease temporally associated with the use of a medicinal product, whether or not considered related to the condition under study and the study product;
- Any abnormality detected during physical examination.

The medical conditions present at the initial trial visit that do not worsen in severity or frequency during the trial will not be defined as AEs but as be considered baseline medical conditions. For the purpose of this trial, disease progression and relapse will be considered as treatment failure, not as an AE.

6.1.1. Severity grading

Adverse signs or symptoms will be graded by the Investigator as mild, moderate, severe or life threatening according to the following definitions:

Grade	Definition
1	Mild : the subject is aware of the event or symptom, but the event or symptom is easily tolerated.
2	Moderate : the subject experiences sufficient discomfort to interfere with or reduce his or her usual level of activity.
3	Severe : significant impairment of functioning: the subject is unable to carry out his or her usual activities.
4	Life threatening or disabling
5	Death related to adverse events

6.1.2. Relatedness

Relatedness will be assessed as defined below based on the temporal relationship between the AE and the treatment, known side effects of treatment, medical history, concomitant medication, course of the underlying disease and trial procedures.

Possibly related: an AE which can medically (pharmacologically/clinically) be attributed to the study treatment.

Unrelated: an adverse even which is not reasonably related to the study treatment. A reasonable alternative explanation must be available.

An AE that is determined to be related to the administration of a study product is referred to as an “adverse drug reaction.”

6.1.3. Expectedness

Expected adverse drug reaction: Any AE possibly related to the administration of mebendazole reported in the literature or on the drug package leaflet and listed in the consent form. These AEs are detailed in the drug package leaflet (Appendix 4).

Unexpected adverse drug reaction: Any AE possibly related to the study product administration, the nature, frequency, specificity or severity of which is unanticipated and not consistent with the available risk information described for these drugs.

6.1.4. Serious adverse events (SAEs)

According to the ICH “Clinical Safety Data Management: Definitions and standards for expedited Reporting E2A” [31], a serious adverse event (SAE) includes any event (experience) or reaction in any untoward medical occurrence that at any dose:

- Results in death;
- Is life threatening, meaning, the subject was, in the view of the Investigator, at immediate risk of death from the reaction as it occurred, *i.e.* it does not include a reaction that, had it occurred in a more serious form, might have caused death;
- Results in persistent or significant disability/incapacity, *i.e.* the event causes a substantial disruption of a person’s ability to conduct normal life functions;
- Requires in patient hospitalisation or prolongation of existing hospitalisation;
- Creates a congenital anomaly or birth defect (not relevant for this study);
- Is an important medical event, based upon appropriate medical judgment, that may jeopardize the patient or subject or may require medical or surgical intervention to prevent one of the other outcomes defining serious.

A “severe” adverse event does not necessarily meet the criteria for a “serious” adverse event (SAE). SAE are reported from consent to 24 hours post-treatment. SAE that are still ongoing at the end of the study period will be followed up to determine the final outcome. The causality of any SAE that occurs after the study period and its possible relatedness to the study treatment or study participation will also be assessed by investigators as described in section 6.1.2.

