Key inclusion / exclusion criteria	
Inclusion: preschool- and school-aged children (3-12 years) with hookworm with at least two slides of quadruplicate Kato-Katz thick smears positive and infection intensities of at least 50 eggs per gram of stool (EPG), with written informed consent signed by the caregiver, able and willing to be examined by a study physician before treatment and to provide two stool samples at baseline.
 
Exclusion: pregnant, any abnormal conditions or history of major systemic or chronic illnesses, severely anaemic (Hb < 80 g/l), received anthelmintic treatment or metronidazole within the past four weeks, or is attending any other clinical trial during this

	study.
Primary endpoints	ERRs on hookworm, assessed 14-21 days post treatment
Secondary endpoints	CRs against hookworm, assessed 14-21 days post treatment CRs and ERRs against A. lumbricoides and T. trichiura Safety, assessed 14-21 days post treatment Acceptability and age-appropriateness of the tablets, assessed during treatment
Exploratory endpoints	Caregivers understanding of the clinical trial in general and by caregiver group, assessed during the informed consenting procedure
Interim analyses	None
Study duration	12 weeks total; up to 10 weeks per participant
Schedule	02/2019 of first-participant in (planned) 05/2019 of last-participant out (planned)
Study site	Wawi, Mvumoni, Bwagamoyo, Piki and Mzambarauni schools, Pemba, Tanzania
Measurements & procedures	A first stool sample will be collected and if the participant is found positive for hookworm a second stool sample will be requested, if possible the next day. The medical history of the participating individuals will be assessed with a standardized questionnaire contained in the case report form, in addition to a clinical and physical examination carried out by the study physician before treatment. This examination also includes pricking subjects' fingers to measure haemoglobin (Hb) levels and, in the case of female participants aged ≥ 10 years, a urine pregnancy test. Randomization of participants into the two treatment arms will be stratified according to intensity of infection. Participants will be interviewed before treatment for clinical symptoms and 3, and 24 hours after treatment to assess occurrence of adverse events (AEs). The efficacy of the treatment will be determined 14-21 days post-treatment by

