4.1. Primary and secondary endpoint

The **primary endpoint** of the study is the ERRs of these two formulations of mebendazole against hookworm assessed before and 14 to 21 days post-treatment using the duplicate Kato-Katz technique. **Secondary endpoints** are the CR against hookworm, CRs and ERRs against *A. lumbricoides* and *T. trichiura* (assessed 14-21 days post-treatment), safety (assessed 3 and 24 hours post-treatment), and acceptability and age-appropriateness of the two formulations of mebendazole (assessed during treatment). **Exploratory endpoints** are how well caregivers understood the clinical trial's informed consent form and its content, and which of the informing methods increase caregivers understanding the most (assessed during the informed consenting process).

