4.6. Schedule of visits

Table 1 briefly presents the distribution of tasks along the trial.

Table 1. Schedule of visits during treatment period.

	Baseline	Examination/Treatment/Safety			Follow-up	
	Days -35 to -1/0	0	Hours 3	24	Days 14 to 21	Days 22 to 29
Sample collection and diagnosis	X				X	
Informed consent	X					
Caregiver questionnaires	X					
Demographics	X					
Medical History		X				
Physical and clinical examination		X				
Hb level and pregnancy assessment		X				
Randomization and treatment		X				

Capturing AEs/ SAEs	X	X	X*
Administration of ALB+IVM (if still infected at follow-up)			X
Observational sheet	X		

* Passive collection of AEs/SAEs (only when a child/caregiver contacts a staff member).

5. Selection of the trial subjects

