6.2. Methods of recording and assessing adverse events

Patients will be kept for observation for 3 hours following treatment for any acute AEs. 3h post-treatment participants will be actively questioned about any unfavorable changes in

the subject's condition. Any reported changes will be recorded as an AE, whether reported by the subject or observed by the Investigator. In case of any abnormal finding, the local study physician will perform a full clinical examination and findings will be recorded. An emergency kit will be available on site to treat any medical conditions that warrant urgent medical intervention. In addition, patients will be also interviewed by a nurse and/or a physician about the occurrence of AEs 24 hours. Information on all AEs (onset, duration, intensity and causality) will be immediately entered in the appropriate AE module of the CRF which is considered as a source document, regardless of whether they are thought to be associated with the study or the drug under investigation. Associated with the use of the drug means that there is a reasonable possibility that the event may have been caused by the drug (see also relatedness definitions below). For all AEs, sufficient information will be pursued and/or obtained so as to permit (i) an adequate determination of the seriousness of the event (i.e. whether the event should be classified as a SAE), (ii) an assessment of the casual relationship between the AE and the study treatments (i.e. whether the event should be classified as an adverse drug reaction), and (iii) an assessment of intensity of AEs by the study physician. Additionally, participants will be encouraged to notify study staff of any AEs that may occur outside of scheduled safety assessments. All SAEs, unexpected adverse drug reactions, or SUSARs must be reported as described in Section 6.3.

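### Section 6.1.4 closes SAE reporting 24 hours after treatment, which contradicts sections 6.2 and 6.3 and the Table 1 footnote; one defined window is needed

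*Combined protocol and SAP*

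**What the plan says.** Section 6.1.4 gives the only explicit SAE window in the protocol: "SAE are reported from consent to 24 hours post-treatment". It then adds two provisions tied to a study period. First, "SAE that are still ongoing at the end of the study period will be followed up to determine the final outcome". Second, investigators are to judge causality for SAEs that arise once that period is over. Neither this section nor any other says when the study period ends.

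Other current text sets no such limit:

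- Section 6.2 encourages participants to tell staff about AEs arising between scheduled assessments, and states: "All SAEs, unexpected adverse drug reactions, or SUSARs must be reported as described in Section 6.3".
- Section 6.3 requires any kind of SAE to be notified to the PI and co-PI within 24 hours of awareness. The clock starts at awareness, and onset is not restricted.
- Section 4.6, Table 1, has a row "Capturing AEs/ SAEs" with three marks. The third is footnoted "Passive collection of AEs/SAEs (only when a child/caregiver contacts a staff member").

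The timing of the safety endpoint is stated in two ways. The synopsis lists "Safety, assessed 14-21 days post treatment", while section 4.1 has "safety (assessed 3 and 24 hours post-treatment").

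**The concern.** Safety and tolerability is a secondary objective in children aged 3 to 12, and the trial stays in contact with them until the follow-up stool samples. A hospitalisation in that interval would meet the SAE definition. Someone who takes the window from 6.1.4 would conclude that it need not be reported. Someone who works from 6.2 and 6.3 would notify the PI and co-PI within 24 hours, and the committee reports of 6.4 would follow.

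Two members of staff could thus treat the same event differently while each follows the protocol. Treatment is open-label, so the person deciding may know the child's arm. Nothing suggests that this would be misused, but an SAE count should not rest on a choice between sections. A final statement that no SAE occurred would also be ambiguous, because it could refer to the first day after treatment or to the whole follow-up.

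**Working it through.** There is no sample size, power or error rate to reproduce. The check is a comparison of the provisions, using an SAE with onset on day 5 as the test case.

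| Place | Limit on timing | SAE with onset on day 5 |
|---|---|---|
| 6.1.4, reporting sentence | closes 24 hours after treatment | outside the window |
| 6.1.4, study-period sentences | undefined period | depends on the reading (see below) |
| 6.2 | none | must be reported |
| 6.3 | none on onset | notify within 24 hours of awareness |
| 6.4 | none on onset | reported to authorities and committees |
| Table 1, third mark | after the active contacts | collected if the child or caregiver makes contact |

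**Position of the third mark.** The column alignment of Table 1 is lost in the text I worked from. The introduction to section 6 and section 6.2 make the 3-hour and 24-hour contacts active, so a mark for passive collection can sensibly stand only after them. Its last day cannot be read.

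**Can 6.1.4 be reconciled with the rest?** One attempt is to read its sentence as describing active questioning only. That fails, because the sentence speaks of reporting and starts at consent, before any post-treatment contact.

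**Do the study-period sentences close the gap?** Two readings are possible.

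1. The study period ends at 24 hours. The day-5 SAE then falls after it and receives a causality assessment, but 6.1.4 attaches no reporting duty.
2. The study period ends at the day 14-21 visit. The day-5 SAE then falls inside it, so the provision for later SAEs does not reach it. It is followed for outcome only if still ongoing at the end, and it remains outside the reporting window.

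Section 5.6 uses the same term for the time up to the last follow-up stool examination, and section 6.1 defines an AE by the course of the study. Both favour the second reading, but neither is a definition, and 6.1.4 leaves a gap under either.

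**Length of the disputed interval**, counted from the 24-hour limit (day 1):

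- to the earliest follow-up day: 14 − 1 = 13 days
- to the latest follow-up day: 21 − 1 = 20 days
- to the last day shown in Table 1: 29 − 1 = 28 days

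**The case against.** The strongest reply is that one loose sentence is being set against several sections that work. Section 6.3 has its own trigger, 6.2 refers to it without a time limit, 6.4 adds no onset limit, and 6.1.4 itself looks beyond the study period. This stands. A reader might infer that an SAE after day 1 would trigger no notification and no committee report. The documents do not support that inference, because a late SAE is outside one sentence and not outside the protocol.

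Other points also stand:

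- Section 6.2 names no end day, so it cannot be cited for a window ending at day 14-21.
- The synopsis line on safety at 14-21 days concerns the timing of an endpoint. It conflicts with 4.1 and with the synopsis's own description of interviews at 3 and 24 hours. This is a separate inconsistency and no evidence of an intended SAE window.
- A reader might convert the interval into a share of follow-up, 13/14 = 93% to 20/21 = 95%, and take it as risk missed. It is a share of calendar days only. The documents give no distribution of SAE onset after a single dose.
- A reader might also attach an upper 95% bound of 3/200 = 1.5% per arm to an observed count of zero. The arithmetic is right, but no such analysis is planned. Section 8.3 plans only a descriptive before-and-after comparison of AE proportions.

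None of this reconciles 6.1.4 with 6.2, 6.3 and Table 1.

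**Conclusion.** The contradiction holds and should be corrected. By its own words, 6.1.4 excludes SAEs that 6.2 and 6.3 require to be reported and that Table 1 expects to collect passively. The conflict covers 13 to 20 days up to the follow-up visit, or 28 days to the end of Table 1. Its practical effect is uncertainty about whether a given late SAE is notified and counted. The documents give no basis for saying how many events this would affect.

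The conclusion rests on two assumptions: that the third AE/SAE mark in Table 1 lies after the 24-hour contact, and that no definition of the study period stands in the appendices, whose content is not reproduced. The conflict between 6.1.4 and 6.2/6.3 does not depend on either.

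**What to change.** 1. In 6.1.4, replace the 24-hour limit with one SAE reporting window running at least through the day 14-21 follow-up visit. State it consistently in 6.2, 6.3 and Table 1.
2. Make the window the same for every participant regardless of treatment outcome. Ending it at the last scheduled contact would not achieve this: the later contact in Table 1 is for treating children still infected, so window length would depend on the efficacy result.
3. Define the study period to match, so that the provisions on ongoing and later SAEs have a clear starting point.
4. Separately, reconcile the safety endpoint timing in the synopsis with section 4.1. Active AE assessment at 3 and 24 hours can coexist with a longer SAE window, so 4.1 need not repeat that window.
5. Optionally, add an AE/SAE question at the day 14-21 stool visit, so that late events do not depend solely on families making contact. This is a low-cost addition and is not needed to remove the contradiction.

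The cost is mainly procedural. A changed reporting window is neither logistical nor administrative, so under section 9.1 the amendment needs ethics committee approval before use. The text changes are short. The optional question would add one CRF item at a visit that already takes place.

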6.1.5. Suspected unexpected serious adverse events (SUSARs)

A suspected unexpected serious adverse reaction (SUSAR) is an unexpected adverse drug reaction which also meets the definition of SAE.

6.2. Methods of recording and assessing adverse events

Patients will be kept for observation for 3 hours following treatment for any acute AEs. 3h post-treatment participants will be actively questioned about any unfavorable changes in

the subject's condition. Any reported changes will be recorded as an AE, whether reported by the subject or observed by the Investigator. In case of any abnormal finding, the local study physician will perform a full clinical examination and findings will be recorded. An emergency kit will be available on site to treat any medical conditions that warrant urgent medical intervention. In addition, patients will be also interviewed by a nurse and/or a physician about the occurrence of AEs 24 hours. Information on all AEs (onset, duration, intensity and causality) will be immediately entered in the appropriate AE module of the CRF which is considered as a source document, regardless of whether they are thought to be associated with the study or the drug under investigation. Associated with the use of the drug means that there is a reasonable possibility that the event may have been caused by the drug (see also relatedness definitions below). For all AEs, sufficient information will be pursued and/or obtained so as to permit (i) an adequate determination of the seriousness of the event (i.e. whether the event should be classified as a SAE), (ii) an assessment of the casual relationship between the AE and the study treatments (i.e. whether the event should be classified as an adverse drug reaction), and (iii) an assessment of intensity of AEs by the study physician. Additionally, participants will be encouraged to notify study staff of any AEs that may occur outside of scheduled safety assessments. All SAEs, unexpected adverse drug reactions, or SUSARs must be reported as described in Section 6.3.

6.3. Reporting of serious adverse events

Any study-related unanticipated problem posing risk of harm to subjects or others (including all unexpected adverse drug reactions), and any type of SAE will be immediately (within a maximum of 24 hours after becoming aware of the event) notified to the study PI and co-PI:

[name]. [name] (PI)

Swiss Tropical and Public Health Institute

[name]

[contact]

[contact]

E-mail: [contact]

[name] (Co-PI)

Public Health Laboratory Ivo de Carneri

[name]

[contact]

[contact]

[contact]

E-mail: [contact]

Within the following 48 hours, the local co-PI must provide to study PI further information on the SAE or the unanticipated problem in the form of a written narrative. This should include a copy of a completed SAE form, and any other diagnostic information that will assist the understanding of the event. In exceptional circumstances, a SAE may be reported by telephone. In these cases, a written report must be sent immediately thereafter by fax or e-mail. Names, addresses and telephone for SAE reporting will be included in the trial-specific SAE form. Relevant pages from the CRF may be provided in parallel (e.g., medical history, concomitant medications).

6.4. Safety reporting to health authorities and ethic committees

The PI will send appropriate safety notifications to Health Authorities in accordance with applicable laws and regulations. Additionally, this information will be provided to the 'Ethik Kommission Nordwest- und Zentralschweiz' (EKNZ, Switzerland) and 'Zanzibar Health Research Institute (ZHRI, Tanzania) according to national rules. Fatal or life-threatening SAEs or SUSARs will be reported within 24 hours to ZHRI, followed by a complete report within 7 additional calendar days. Other SAEs and SUSARs that are not fatal or life-threatening will be filed as soon as possible but no later than 14 days after first knowledge by the sponsor.

7. Data management and data quality control

7.1. Source data

Source data are the clinical findings and observations, laboratory data maintained at the study site. Source data are contained in source documents. Local authorities are allowed to access the source data. Source data will be entered directly onto different documents:

- **CRF** where all the clinical and physical examination data, together with treatment information, adverse events and follow-up results are recorded. Each subject enrolled into the clinical study will have a CRF. One of the investigators will review, and approve each completed CRF. All data requested on the CRF must be recorded.

- **Laboratory parasitology sheets** where egg counts for each STH species are recorded.
- **Observational sheet** which an observer will record every child's reaction to treatment (age-appropriateness). Every participant who received treatment will have an observational sheet.
- **Acceptability questionnaire and observation** which the participant responds to if aged between 6-12 years and a staff member fills out (the observation section) for all participants.
- **Consent questionnaire** which every caregiver will respond to assess their understanding of the study their child is enrolled in. This also includes socioeconomic data (asset possession).

All source data documents will be kept for at least 15 years. The study site will retain a copy of the documents to ensure that local collaborators can provide access to the source documents to a monitor, auditor, or regulatory agency.

7.2. Data collection and documentation

Collected data will fall into one of the following categories:

- a) Anthropometric and clinical characteristics of the trial participants collected using the study's CRF such as weight, height, blood pressure, temperature, pregnancy status (for female subjects ≥ 10 years of age), overall health status and any abnormal medical condition or disease.
- b) Egg counts of hookworm (*Necator americanus* and *Ancylostoma duodenale*, the differentiation of the two species will not be made), *T. trichiura* and *A. lumbricoides*.
- c) Observational data concerning the child's receptivity to the tablet.
- d) Participant answers to the acceptability and adequacy questionnaire.
- e) Asset possession and household characteristics of each participant.
- f) Caregivers' answers to the knowledge assessment questionnaire.

Data in above categories (a) and (b) will be paper-captured, whereas data in categories (c), (d), (e) and (f) will be collected directly into tablets using Open Data Kit (ODK; free electronic data collection software) and uploaded to a server hosted at Swiss TPH. In paper-based data collection, all missing data must be explained. If a space on the CRF is left blank because the procedure was not done or the question was not asked "N/D" will be entered. If the item is not applicable to the individual case "N/A" will be written. All entries will be printed in black ink. All corrections must be initialled and dated. Paper-captured data will be subsequently double entered, using the EpiInfo data entry template, into ACCESS data

entry masks by two independent staff members for quality assurance. The EpiInfo mask will be tested before use. Both databases will then be cross-checked using the Data Compare utility of EpiInfo; any discrepancies will be corrected by consulting the hard copy. Data will be entered at the study site. Data entered into ACCESS databases will only be accessible to authorized personnel directly involved with the study by use of a password. All data will be exported and saved in the following formats: .mdb, .xlsx and .csv. Hard copies of the data such as parasitological sheets and CRFs will remain at PHL-IdC. Digital copies along with the databases will be transferred to the Swiss TPH after a Material Transfer Agreement has been signed by both the Swiss TPH and PHL-IdC. Data will then be analyzed as described in section 8.

